9.2.1 Adverse events of special interest (AESI)

An adverse event of special interest is a grouping of adverse events that are of scientific and medical concern specific to compound midostaurin. These groupings are defined using MedDRA terms, SMQs (standardized MedDRA queries), HGLTs (high level group terms), HLT (high level terms) and PTs (preferred terms) in the Case Retrieval Sheet. For each specified AESI, number and percentage of patients with at least one event of the AESI occurring will be summarized. A listing of all grouping levels down to the MedDRA preferred terms used to define each AESI will be generated.

9.3 Laboratory data

On analyzing laboratory assessments, data from all sources (central and local laboratories) will be combined. The summaries will include on-treatment laboratory assessments.

The following summaries will be produced for the laboratory data (by laboratory parameter):

- Shift tables using CTC grades to compare baseline to the worst post-baseline value will be produced for hematology and biochemistry laboratory parameters with CTC grades.

For laboratory parameters where CTC grades are not defined.

- Shift tables to the worst post-baseline value will be produced using the low/normal/high classifications based on laboratory reference ranges.

Liver function parameters

Liver function parameters of interest are total bilirubin (TBIL), Alanine transaminase (ALT) and enzymes aspartate transaminase (AST). The number (%) of patients with worst post-baseline values as per Novartis Liver Toxicity guidelines will be summarized:

- ALT or AST > 3xULN
- ALT or AST > 5xULN
- ALT or AST > 8xULN
- ALT or AST > 10xULN
- ALT or AST > 20xULN
- TBIL > 2xULN
- TBIL > 3xULN
- ALT or AST > 3xULN & TBIL > 2xULN

9.4 ECG and cardiac imaging data

Analyses of QT prolongation will be based on QTcF measurement. In general, QTcF would be referred to as QTc throughout the document.

Baseline definition

Baseline is defined from pre-dose ECGs performed on Cycle 1 Day 1 if available. Otherwise, the pre-dose ECG measurements taken on most recent day prior to the start of any study treatment within 14 days is considered as baseline. Unscheduled visits are included.

Population for analysis

Notable ECG assessments:

Patients will be considered evaluable (included in “Total”) for outlier analysis if they are at risk at baseline and have at least one post-baseline ECG measurement. For change from baseline analyses they have to have at least one baseline ECG measurement and one post-baseline measurement.

A patient is considered at risk at baseline, if the baseline of this patient is missing or:

- ≤ 450 ms for abnormality “value of > 450 ms and ≤ 480 ms”
- ≤ 480 ms for abnormality “value of > 480 ms and ≤ 500 ms”
- ≤ 500 ms for abnormality “value of > 500 ms”

QTc analysis

QTc analysis will be mainly based on QTcF and QTcB. Notable abnormalities will be summarized for the following:

- An increase of 30 to 60 ms in QTcF (and QTcB)
- An increase of > 60 ms in QTcF (and QTcB)
- Patients with any QTcF/QTcB value of > 450 and ≤ 480 ms
- Patients with any QTcF/QTcB value of > 480 and ≤ 500 ms
- Patients with any QTcF/QTcB value of > 500 ms

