4.1 Description of study design

This is a randomized, double-blind, multi-center, placebo-controlled phase III study of midostaurin (PKC412) or placebo in combination with idarubicin/daunorubicin and cytarabine for induction therapy, intermediate-dose cytarabine for consolidation therapy, followed by post-consolidation therapy with midostaurin or placebo in adult patients with newly diagnosed FLT3-MN (SR<0.05) AML, i.e., FLT3 mutant to wild type signal ratio below the 0.05 clinical cut-off. The study is designed to evaluate the efficacy and safety of midostaurin combined with intensive chemotherapy in this indication. 502 adult patients with newly diagnosed AML demonstrating FLT3-MN (SR<0.05) as determined by a Novartis designated laboratory will be enrolled at approximately 150-180 sites worldwide.

Figure 4-1 Study Design

Eligible and consented patients are allowed to start with the 7+3 chemotherapy immediately after the unequivocal diagnosis of AML; the day of the first dose of chemotherapy is defined as Day 1.

Patients will be tested for the absence of FLT3-ITD and FLT-TKD mutations, using a validated clinical trial assay in a Novartis designated laboratory. Absence of mutation is defined as ITD and TKD activating mutations at codons D835 and I836 in the FLT3 gene, below the clinical cutoff of 0.05 mutant to wild type signal ratio.

Patients with confirmed FLT3-MN (SR<0.05) AML will be randomly assigned 1:1 to midostaurin or placebo by using a stratified randomization according to age (<60 vs. ≥60 years), Patients will be randomized on Day 8, i.e., the day of the first dose of midostaurin or placebo. Patients with a FLT3 mutation or with an unknown FLT3 mutation status by study Day 8 will be considered as molecular screening failures and cannot be randomized.

Provided that FLT3-MN (SR<0.05) status has been confirmed, patients meeting all other eligibility criteria will start the administration of midostaurin or placebo on Day 8.

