6.1 Study treatment

In this study, the term “Study drug” refers to midostaurin/placebo labeled as PKC412/placebo provided as 25 mg capsules which are packaged in blister packs and supplied by Novartis as double-blind supplies.

The term “Study treatment” will indicate treatment with daunorubicin/idarubicin, cytarabine, or midostaurin/placebo.

Induction chemotherapy will start on Day 1 and the randomization and treatment start with midostaurin/placebo will be done on Day 8 when (molecular) eligibility has been confirmed based on the absence of a FLT3 mutation as determined by a Novartis designated laboratory. If the patient does not have FLT3 test results qualifying for eligibility by Day 8 then the patient will be considered as a molecular screening failure and cannot be randomized.

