7.1.2 Screening

Written informed consent must be obtained prior to any screening procedures. Screening assessments to confirm eligibility into the study should be performed as per visit evaluation schedule between Day-14 and Day-1. Serum pregnancy test must be conducted within 72 hours prior to start of study treatment and must be confirmed negative before the first dose of study treatment. ECG should be obtained within 3 days prior to start of study treatment. Local measurements of $QTc \geq 480ms$ will be centrally verified on a copy of a high quality recording that includes time and voltage scales.

As part of screening procedures, a bone marrow aspirate or a whole blood sample will be collected and shipped immediately to a Novartis designated laboratory for FLT3 mutation assessment. In case both sample types are collected/available, FLT3 screening will be preferentially performed only on the bone marrow sample; and the peripheral blood sample will be banked for future testing.

Assessments done within four days prior to Day 1 (start of chemotherapy) as per local practice or under a local protocol, prior to signing the study specific informed consent form and start of screening for the study, will not have to be repeated and results can be used for the study. At the discretion of the investigator, the final diagnosis of AML by bone marrow aspirate can be confirmed after the informed consent form has been signed for the study.

In some specific cases (and with Novartis' prior approval), the FLT3 status may have been determined prior to screening in a Novartis validated laboratory. In such cases, this previously obtained FLT3 result will be used for the study. Part of the remaining bone marrow sample should be provided to Novartis for further analyses defined in the protocol. [REDACTED]

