7.2.2.7 Cardiac assessments

7.2.2.7.1 Electrocardiogram (ECG)

A standard triplicate 12 lead ECG each 2 min apart will be performed according to the relevant Visit Evaluation Schedule ([Table 7-1](#) and [Table 7-7](#)).

[figure not shown]

Table 7-7 Local ECG assessment monitoring schedule

	Day	Time	ECG Type
Screening	-3 to -1	Pre-dose	12 Lead
Induction Phase 1	Day 8, Day 11, Day 21	Pre-dose (before PK) Post-dose at 3 hours ± 0.5 hour (before PK)	12 Lead
Consolidation Phase, each cycle	Day 4, Day 17	Pre-dose (before PK) Post-dose at 3 hours ± 0.5 hour (before PK)	12 Lead
Prior to 1 st cycle of post-consolidation		Pre-dose (before PK)	12 Lead,
Post-consolidation, cycle 2 to cycle 12	Day 1	Pre-dose (before PK)	12 Lead
Post-consolidation, cycle 12 or at EOT (at any phase of the study)	Day 28	Pre-dose (before PK) Anytime	12 Lead 12 Lead
Unscheduled sample		Anytime when clinically indicated	12 Lead

Interpretation of the tracing must be made by a qualified physician and documented on the CRF. Each ECG tracing should be labeled with the study number, patient initials (where regulations permit), subject number, date, and kept in the source documents at the study site. Clinically significant abnormalities present at screening should be reported on the Medical History CRF.

Standard 12 lead ECG recording will be performed after the patient has been resting for approximately 10 min prior to each ECG collection time point indicated in [Table 7-7](#) and prior to PK samples. Local measurements of $QTc \geq 480ms$ shall be centrally verified on a copy of the original high quality recording that includes time and voltage scales.

Dose adjustments in case of QT prolongation should be performed per [Section 6.3](#).

[figure not shown]
Clinically significant ECG abnormalities present at screening should be reported on the Medical History CRF. New or worsened clinically significant findings occurring after informed consent must be recorded on the Adverse Events CRF.

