3.5 Date of first administration of study treatment

The date of first administration of study treatment is derived as the first date when a non-zero dose of any component of study treatment was administered and recorded on the exposure eCRF. For example, if the 1st dose of study drug A is administered on 04Jan2019, and the 1st dose of its combination partner, drug B, is administered on 03Jan2019, the date of the first administration of study treatment is on 03Jan2019). The date of the first administration of study treatment will also be referred as the *start of study treatment*.

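### The SAP takes its QTc baseline from a Cycle 1 Day 1 ECG that is not scheduled, so the Day 8 ECG recorded before any midostaurin/placebo counts as post-baseline

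*SAP*

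**What the plan says.** The first choice of QTc baseline in SAP Section 9.4 is: "Baseline is defined from pre-dose ECGs performed on Cycle 1 Day 1 if available". The second choice follows: "Otherwise, the pre-dose ECG measurements taken on most recent day prior to the start of any study treatment within 14 days is considered as baseline". The section then adds: "Unscheduled visits are included".

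Protocol Table 7-7 (Section 7.2.2.7.1) has a screening ECG on Day -3 to -1. Its next row, Induction Phase 1, lists "Day 8, Day 11, Day 21", each with a pre-dose recording and one at 3 hours post-dose, and the section requires triplicate ECGs. Section 7.1.2 gives the same screening window: "ECG should be obtained within 3 days prior to start of study treatment".

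On timing, Protocol Section 4.1 says "the day of the first dose of chemotherapy is defined as Day 1", and Section 6.1 says "Induction chemotherapy will start on Day 1 and the randomization and treatment start with midostaurin/placebo will be done on Day 8". SAP Section 3.5 dates the start of study treatment from "the first date when a non-zero dose of any component of study treatment was administered", and SAP Section 3.2 counts chemotherapy as a component. The on-treatment window in SAP Section 3.6.2 opens on that same date, and SAP Section 9 builds the safety summaries from on-treatment data.

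**The concern.** The visit named as first-choice baseline has no ECG scheduled. The rule therefore usually selects the screening ECG, and the change from baseline spans a week of chemotherapy and supportive care before study drug begins.

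The Day 8 pre-dose triplicate is the last recording before the arms can differ. The plan collects it but treats it as an outcome. A QTcF above 500 ms, or a rise of more than 60 ms, at that recording enters the table of notable abnormalities under midostaurin or placebo.

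QT is a study-drug question in this protocol. Table 6-2 and Section 6.3.2 link midostaurin/placebo dosing to QTcF, and Section 10.5.4 names QT among the exposure-response safety endpoints. Days 1 to 7 can also move QTc without study drug. Section 6.4.1 permits antibiotic and antifungal prophylaxis, and Appendix 1 includes levofloxacin, fluconazole and ondansetron among drugs with a known QT risk. What is at stake is whether the QTc tables can be read as evidence about midostaurin.

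**Working it through.** The plan states no figure for this point, so the check sets the definitions against the schedule.

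1. **Is there a Cycle 1 Day 1 ECG?** Table 7-7 goes from screening to Day 8. Scheduled ECGs on Day 1: 0. (Table 7-1 is damaged in the text available, but its ECG row refers to Table 7-7, which is intact.)
2. **What does the rule select instead?** It selects the most recent ECG before the start of any study treatment, within 14 days. The protocol requires a screening ECG within 3 days. The two windows are compatible, so a patient who follows the schedule gets the screening ECG. An unscheduled pre-dose Day 1 ECG would take precedence.
3. **Can Day 8 pre-dose be the baseline?** No. It comes after the first dose of chemotherapy: cytarabine runs on Days 1 to 7 and the anthracycline on Days 1 to 3.
4. **Is Day 8 pre-dose on-treatment?** Yes, because the window opens on Day 1. SAP Section 9.4 does not define post-baseline for ECGs; the status follows from steps 2 to 4.
5. **How many recordings are affected?** Induction 1 has 3 days × 2 = 6 scheduled time points. One of them, Day 8 pre-dose, precedes the first midostaurin/placebo dose.
6. **Whose count changes?** The number of patients with any notable value rises only through those who are notable at Day 8 pre-dose and at no later ECG. A patient who is notable at both is counted either way.

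**Direction of the effect, on assumed rates.** None of these rates is in the documents. Let p be the proportion with a notable Day 8 pre-dose value, equal in both arms and independent of later values. Let r be the rate after study drug starts, taken as 2% for placebo and 6% for midostaurin (true difference 4.0 points, ratio 3.0). The tabulated rate is p + (1 − p)r, and the tabulated difference is (1 − p) × 4.0 points.

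| p | placebo | midostaurin | difference | ratio |
|---|---|---|---|---|
| 1% | 0.01 + 0.99 × 0.02 = 3.0% | 0.01 + 0.99 × 0.06 = 6.9% | 3.96 points | 2.3 |
| 5% | 0.05 + 0.95 × 0.02 = 6.9% | 0.05 + 0.95 × 0.06 = 10.7% | 3.8 points | 1.55 |
| 10% | 0.10 + 0.90 × 0.02 = 11.8% | 0.10 + 0.90 × 0.06 = 15.4% | 3.6 points | 1.3 |

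Both rates rise and the difference hardly moves. If the same patients are prone to prolongation before and after Day 8, fewer extra patients are added than the formula gives.

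**The case against.** The strongest reply is that a pre-chemotherapy baseline is the plan's consistent safety rule. SAP Section 3.6.1 ties the safety baseline to study treatment and gives ECG as an example. The on-treatment period and the adverse event summaries start at the same dose. Read this way, the QTc tables describe the whole regimen with midostaurin against the whole regimen with placebo, and a long QTc on Day 8 is a true on-study-treatment finding. This stands, and it is a reason to keep that table.

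The Day 1 reference is also conditional and has a workable fallback. Patients entering from trial A2220 begin induction under another protocol (Protocol Section 7.1.2), whose ECG schedule is not in these documents, so some Day 1 ECGs may exist. This stands too: the reference has no scheduled visit behind it, but patients are not left without a baseline.

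Moving the baseline to Day 8 outright would have its own cost. A raised Day 8 value would shrink later increases, and under the at-risk rule in SAP Section 9.4 a patient above 500 ms on Day 8 would leave the denominator for that category. This stands against replacement but not against a second table.

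A reader might infer that the rule biases the comparison in favour of midostaurin, or that it cuts a threefold excess to about 1.6-fold. The documents support neither. Day 8 pre-dose values precede any effect of allocation, so on average they add equally to both arms. The ratio comes only from assumed rates, and SAP Section 9.4 plans summaries of notable abnormalities, with no ratio, test or model.

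**Conclusion.** The point holds as one of attribution and clarity. The first-choice baseline refers to an unscheduled ECG, and one pre-drug recording per patient is tabulated by arm as a post-baseline outcome. Non-drug events are added to both arms, so absolute rates of notable QTc are inflated as a description of the study-drug period. No arm is favoured. The size cannot be computed, because the documents give neither QTc variability nor the shift expected over the first week; the table of assumed rates shows direction only.

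The conclusion assumes that Table 7-7 is the complete ECG schedule and that post-baseline has the meaning implied by SAP Sections 3.6.2 and 9.4. The trial stopped for futility at the first interim analysis, so the consequence is confined to safety reporting in the final CSR. A reader might go further and call the pre-chemotherapy baseline wrong. It is not: it answers a question about the whole regimen and leaves the question about the study drug without a table.

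**What to change.** 1. In SAP Section 9.4, correct the Cycle 1 Day 1 reference: the scheduled pre-treatment ECG is at screening, and an unscheduled pre-dose Day 1 ECG may replace it. Keep this baseline and label the resulting table as the whole-regimen summary.
2. Add a QTc outlier and change-from-baseline summary for midostaurin versus placebo. Baseline is the mean of the Day 8 pre-dose triplicate, or the screening ECG if that is missing. Count only ECGs after the first midostaurin/placebo dose.
3. Show both tables together, with the at-risk denominator for each category, because patients already prolonged on Day 8 drop out of the second table only.
4. State that the second summary was specified after unblinding, since this SAP version followed the futility stop.

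No new data are needed. The cost is one extra table and a few lines of SAP text.

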9.5 Vital signs

Vital sign assessments are performed in order to characterize basic body function. The variables collected in studies: height [cm], body temperature [$^{\circ}$ C], heart rate [beats per minute (bpm)], systolic and diastolic blood pressure [mmHg], and respiratory rate [breaths per minute].

Patients with clinically notable vital sign abnormalities will be summarized and listed and assessments collected later than 30 days after study treatment discontinuation will be flagged in the listings. The criteria for clinically notable abnormalities are depicted in [Table 9-1](#) and [Table 9-2](#).

Table 9-1 Clinically notable elevated vital sign values

Variable	Criteria
Systolic BP	≥ 180 mmHg and an increase ≥ 20 mmHg from baseline

Variable	Criteria
Diastolic BP	≥ 105 mmHg and an increase ≥ 15 mmHg from baseline.
Body temperature	≥ 39.1°C (102.3°F)
Heart rate	≥ 120 bpm with increase from baseline of ≥ 15 bpm
Respiratory rate	≥ 30 bpm

Table 9-2 Clinically notable below normal vital sign values

Variable	Criteria
Systolic BP	≤ 90 mmHg and a decrease ≥ 20 mmHg from baseline
Diastolic BP	≤ 50 mmHg and a decrease ≥ 15 mmHg from baseline
Body temperature	≤ 35°C (95°F)
Heart rate	≤ 50 bpm with decrease from baseline of ≥15 bpm
Respiratory rate	≤ 10 breaths per minute

9.6 Pharmacokinetic endpoints

9.6.1 Exposure to the sum of active moieties

The exposure variable will be derived for all PK exposure endpoints (see [Table 9-3](#); not applicable to Tmax) to consider the contribution of the active metabolites to the total exposure of the compound.

The exposure to the sum of active moieties combines the concentration of the parent- (Midostaurin) and the two active metabolites (CGP52421 and CGP62221) scaled based on their relative potencies, and parent to metabolite molecular weight ratio for AML indication as shown below:

$$Midostaurin + CGP52421 * (0.06) * \frac{Midostaurin\ mwt}{CGP52421mwt} + CGP62221 * (1.40) * \frac{Midostaurin\ mwt}{CGP62221mwt}$$

Where mwt is the molecular weight of each analyte:

- Midostaurin =570.65
- CGP52421=587.23
- CGP62221=556.63

9.6.2 PK parameters

PK parameters for midostaurin and the active metabolites (CGP52421, CGP62221) and sum of active moieties will be determined using non-compartmental method(s) using Phoenix WinNonlin (Version 6.4 or later- Certara L.P.) for the patients who had full PK sampling on Cycle 1 Day 8 of the induction therapy.

PK parameters listed in [Table 9-3](#) will be estimated and reported, when feasible (dependent on sampling scheme, and validity of samples).

Concentration data from patients collected after C1D8 (during induction, consolidation, post-consolidation phases at trough (predose) and C3h according to the PK sampling schedule [see

[Study protocol CPKC412E2301 Table 7-8](#)] will be analyzed where possible, and relevant NCA parameters determined (C_{min}, C_{3h}).

AUC_{0-t} (AUC_{0-12h} at C1D8) and C_{max} are defined as primary parameters (contributing to PAS-full definition).

NCA PK parameters and all concentrations will be summarized and reported. Summary statistics will include n (number of values to be reported), arithmetic and geometric mean, median, SD, CV, geometric CV, minimum and maximum.

Table 9-3 Non-compartmental PK parameters

AUC _{0-t}	The AUC from time zero to a measurable concentration sampling time (t) (mass x time x volume ⁻¹). Note: as the last sampling time is at 12 h, AUC _{0-12h} will be determined after the first dose
AUC _{last}	The AUC from time zero to the last measurable concentration sampling time after the first dose (t _{last}) (mass x time x volume ⁻¹)
C _{max}	The maximum (peak) observed plasma, blood, serum, or other body fluid drug concentration after the first dose administration (mass x volume ⁻¹)
C _{min}	Minimal observed pre-dose concentration (when feasible)
C _{3h}	Concentration at 3 hours post-dose (when feasible)
T _{max}	The time to reach maximum (peak) plasma, blood, serum, or other body fluid drug concentration after single dose administration (time)
¹ For parent drug only ² AUC%Extrap and Rsqadj will be used in the interpretation of the primary PK parameters and therefore will be included in the listings only.	

Descriptive statistics (n, arithmetic mean, CV% mean, standard deviation (SD), median, geometric mean, CV% geo-mean, minimum and maximum) will be presented by treatment for PAS-full for all PK parameters defined in [Table 9-3](#) except T_{max}, where only n, median, minimum and maximum will be presented. All individual PK parameters will be listed using the PAS-all.

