7.2.3 Pharmacokinetics

Serial PK samples will be collected in all patients to assess the plasma concentrations of midostaurin, CGP52421 and CGP62221. To allow a proper description of midostaurin, CGP52421 and CGP62221 pharmacokinetics additional PK samples will be collected in a subset of the first 60 patients randomized into the trial. Therefore there will be approximately 30 patients receiving midostaurin and contributing to the PK analysis. A detailed description of the sample collection is provided in [Table 7-8](#). In this subset of patients, non-compartmental PK parameters will be derived as described in [Section 10.5.4](#).

The PK samples in the other patients will be collected according to the sampling scheme described in [Table 7-9](#).

The whole set of concentrations will also be further analyzed using a population PK approach ([Section 10.5.4](#)).

Table 7-8 Pharmacokinetic blood collection log for Midostaurin, CGP52421 and CGP62221 – Full PK collection (N=60)

Dose Reference ID (2)	PK Sample number	Cycle (Period number)	Study day for each cycle	Time(1)	Blood volume (mL)
1	101	Induction 1 Cycle 1*	8	Pre-dose	3
1	102	Induction 1 Cycle 1*	8	1h	3
1	103	Induction 1 Cycle 1*	8	Post-dose 3hrs +- 0.5 hrs	3
1	104	Induction 1 Cycle 1*	8	6h	3
1/ 111(3)	105	Induction 1 Cycle 1*	8	12h (prior to the evening dose of Midostaurin/ Placebo)	3
2/201	106	Induction 1 Cycle 1	11	Pre-dose	3
2	107	Induction 1 Cycle 1	11	Post-dose 3hrs +- 0.5 hrs	3
3/301	108	Induction 1 Cycle 1	15	Pre-dose	3
4/401	109	Induction 1 Cycle 1	18	Pre-dose	3
5/501	110	Induction 1 Cycle 1	21	Pre-dose	3
5	111	Induction 1 Cycle 1	21	Post-dose 3hrs +- 0.5 hrs	3
6/601	112	Consolidation, cycle 1	4	Pre-dose	3
6	113	Consolidation Cycle 1	4	Post-dose 3hrs +- 0.5 hrs	3

Dose Reference ID (2)	PK Sample number	Cycle (Period number)	Study day for each cycle	Time(1)	Blood volume (mL)
7/701	114	Consolidation, cycle 1	17	Pre-dose	3
7	115	Consolidation, cycle 1	17	Post-dose 3hrs +/- 0.5 hrs	3
8/801	116	Consolidation, cycle 3	4	Pre-dose	3
8	117	Consolidation, cycle 3	4	Post-dose 3hrs +/- 0.5 hrs	3
9/901	118	Consolidation, cycle 3	17	Pre-dose	3
9	119	Consolidation, cycle 3	17	Post-dose 3hrs +/- 0.5 hrs	3
10/1001	120	Prior to 1st of Post-consolidation, cycle 1		Pre-dose [REDACTED]	3
11/1101	121	Post-consolidation, cycle 4	1	Pre-dose	3
11	122	Post-consolidation, cycle 4	1	Post-dose 3hrs +/- 0.5 hrs	3
12/1201	123	Post-consolidation, cycle 7	1	Pre-dose	3
13/1301	124	Post-consolidation, cycle 10	1	Pre-dose	3

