10.5.4 Pharmacokinetics

Plasma concentrations: Plasma concentrations will be summarized by treatment part and time point. Summary statistics will include n (number of values to be reported), arithmetic and geometric mean, median, SD, CV, and geometric CV, minimum and maximum. Concentrations below the LLOQ will be treated as zero in summary statistics except for geometric mean. Zero concentrations will not be included in the geometric mean calculation. For T_{max}, the median and range will be provided.

Non-compartmental analysis (NCA): PK parameters for midostaurin and the active metabolites will be determined using non-compartmental method(s) using Phoenix WinNonlin (Version 6.4 or later- Certara L.P.) for the patients who had full PK sampling on Cycle 1 Day 8 of the induction therapy.

Concentration data from patients who underwent sparse sampling only will be analyzed where possible, and relevant NCA parameters determined.

PK parameters listed in [Table 10-1](#) will be estimated and reported, when feasible (dependent on sampling scheme, and validity of samples).

AUC_{0-t} and C_{max} are defined as primary parameters (contributing to PAS-full definition).

All PK parameters will be determined when possible. In addition, and when feasible, analysis of data from all subjects (frequently and less frequently sampled) for PK parameters at steady state (Table 10-1) will be performed.

NCA PK parameters and all concentrations will be summarized and reported. Summary statistics will include n (number of values to be reported), arithmetic and geometric mean, median, SD, CV, geometric CV, minimum and maximum.

Population pharmacokinetic (PopPK) analysis: the PK samples of the PAS-all will be analyzed using a population PK approach. Comparisons of new data with predicted exposures from existing models will be provided through visual predictive checks (VPCs). Further details of the analysis as well as the results will be reported in a stand-alone analysis plan and report independent of this clinical study report. In addition, comparisons of individual predicted patient parameters with those observed will be conducted and reported in the CSR. Further details will be provided in the SAP.

Exposure-response analyses for relevant efficacy endpoints (including CR, CRi with adequate blood count recovery and EFS, plus investigation of further endpoints such as MRD) and safety endpoints (including QT and AEs) will be further discussed as appropriate in the SAP.

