3.8.3 Pharmacokinetic analysis set

Pharmacokinetic Analysis Set for all (PAS-all)

The Pharmacokinetic analysis set for all (PAS-all) includes all subjects in the safety set, and provide at least one evaluable PK concentration.

For a concentration to be evaluable:

- Dosing information must be properly documented (data and time of administration)
- The planned dose of midostaurin must be taken prior to sampling.
- For pre-dose samples: no vomiting within 4 hours after the midostaurin dose prior to sampling, the sample is collected before the next dose administration.
- For post-dose samples: no vomiting within 4 hours after midostaurin dosing

The PAS-all will be the primary population used for all pharmacokinetic analyses using trough concentration data.

Pharmacokinetic Analysis Set for full PK profile (PAS-full)

The Pharmacokinetic analysis set for full PK profiles (PAS-full) includes all subjects in the PAS-all, who provide an evaluable PK profile. A profile is considered evaluable if all of the following conditions are satisfied:

- Subject receives the planned first dose of midostaurin on C1D8 of Induction therapy
- Subject did not vomit within 4 hours of the first dose of midostaurin on C1D8 of Induction therapy
- Subject provides at least one primary PK parameter (C_{max}, AUC_{0-t})

The PAS-full will be the primary population used for all pharmacokinetic analyses based on full PK profile data.

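### SAP 9.6.2 summarises Cmin and C3h on the full-profile PK set, in conflict with SAP 3.8.3 for Cmin and with Protocol 10.5.4 for both

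*SAP*

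**What the plan says.** SAP 3.8.3 defines two PK sets with separate purposes. For PAS-all: "The PAS-all will be the primary population used for all pharmacokinetic analyses using trough concentration data". For PAS-full: "The PAS-full will be the primary population used for all pharmacokinetic analyses based on full PK profile data". Entry to PAS-full requires the planned first dose on day 8 of induction, no vomiting within 4 hours of that dose, and a third condition: "Subject provides at least one primary PK parameter", meaning Cmax or AUC0-t.

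SAP 9.6.2 does not keep that separation. Its descriptive statistics "will be presented by treatment for PAS-full for all PK parameters defined in" Table 9-3, with a shorter list of statistics for Tmax. Table 9-3 lists AUC0-t, AUClast, Cmax and Tmax, which belong to the first dose. It also lists Cmin (the smallest observed pre-dose concentration) and C3h (the concentration 3 hours after dosing), which can be obtained at later visits.

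The same section derives non-compartmental parameters for patients with full sampling on day 8. It determines Cmin and C3h from later samples with a reference to Protocol Table 7-8 only. It summarises all concentrations without naming a set, and lists individual parameters on PAS-all.

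Protocol 7.2.3 limits full sampling to the first 60 patients randomised: "Therefore there will be approximately 30 patients receiving midostaurin and contributing to the PK analysis". All other patients follow the sparse schedule in Table 7-9. Protocol 10.5.4 gives those patients a place in the parameter analysis: "Concentration data from patients who underwent sparse sampling only will be analyzed where possible, and relevant NCA parameters determined". It adds that, when feasible, steady-state parameters will be analysed in frequently and less frequently sampled subjects together.

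**The concern.** For Cmin, both SAP instructions cannot be followed. A programmer working from 9.6.2 would build the table on PAS-full, and one working from 3.8.3 would build it on PAS-all.

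The choice matters because the AUC, Cmax and Tmax entries in Table 9-3 describe the first dose only. Cmin and C3h are the only parameters in the table that describe exposure after day 8. Characterising the pharmacokinetics is a stated secondary objective. Protocol 2.3 explains that this trial doses beyond the approved days 8 to 21 of each cycle, so later exposure is the new information. SAP 9.6.1 also derives the sum of active moieties for the same parameters, so its Cmin and C3h summaries would carry the same restriction.

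**Working it through.** **1. Which set each parameter belongs to**

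| Parameter | SAP 3.8.3 | Protocol 10.5.4 | SAP 9.6.2 |
|---|---|---|---|
| AUC0-t, AUClast, Cmax, Tmax (first dose) | PAS-full | Full-sampling patients | PAS-full: consistent |
| Cmin (pre-dose) | PAS-all, as trough data | Sparse patients where possible; all subjects at steady state | PAS-full: conflicts with both |
| C3h (post-dose) | Not assigned: neither a trough nor a full profile | As for Cmin | PAS-full: departs from the protocol only |

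**2. Who is in PAS-full**

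Entry needs Cmax or AUC0-t. SAP 9.6.2 derives non-compartmental parameters for patients with full day-8 sampling, so in effect PAS-full is drawn from that subset. This is an inference, since 3.8.3 does not itself require the full schedule.

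**3. Size of the subset**

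Inputs: 60 full-sampling patients (Protocol 7.2.3) and 1:1 allocation.

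60 × 1/2 = 30 on midostaurin, which reproduces the protocol's own figure.

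**4. Share of midostaurin patients outside it**

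Share = 1 − 30/(N/2), where N is the number randomised. The planned N is 502. The trial stopped after the first interim analysis, and neither document gives the number actually randomised. SAP 9.13.1 expected at least 283 at that analysis, planned at 114 events; it took place with 145.

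| N randomised | Midostaurin arm, N/2 | In subset | Outside subset |
|---|---|---|---|
| 283 | 141.5 | 21.2% | 78.8% |
| 350 | 175 | 17.1% | 82.9% |
| 400 | 200 | 15.0% | 85.0% |
| 502 | 251 | 12.0% | 88.0% |

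On PAS-all, the midostaurin patients available for Cmin would rise from about 30 to at most about 141 (N = 283) or 251 (N = 502). These are upper limits, because PAS-all requires membership of the safety set and at least one evaluable concentration.

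**5. Loss within the subset**

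PAS-full removes a patient who vomited within 4 hours of the first dose. PAS-all judges evaluability sample by sample, so later samples from that patient can still count. An event on day 8 of induction has no bearing on a consolidation Cmin.

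**6. What the sparse schedule supplies**

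Table 7-9 has pre-dose samples in induction and consolidation, before post-consolidation, and at post-consolidation cycles 4, 7, 10 and the end of cycle 12. Its 3-hour samples are in induction and consolidation only. The single post-consolidation 3-hour sample, at cycle 4, is in Table 7-8. Moving C3h to PAS-all therefore adds sparse patients in induction and consolidation, and none afterwards.

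**The case against.** The strongest reply is that little is lost. SAP 9.6.2 still summarises all concentrations and lists individual parameters on PAS-all. C3h is itself a concentration and Cmin is an observed one, and population PK uses the PAS-all samples under a separate plan (Protocol 10.5.4). This stands, and it limits the point to one descriptive table. It does not remove it: no set is named for the concentration summaries, a listing is not a summary, and the parameter table would cover fewer patients than its own listing.

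Second, C3h is not a trough, so SAP 3.8.3 does not place it in PAS-all. That also stands. For C3h the conflict is with Protocol 10.5.4 alone, whose commitments carry the qualifiers of possibility and feasibility.

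Third, the reference to Table 7-8 alone proves little. After day 8 that table contains every scheduled time point of Table 7-9, and the sentence does not limit itself to full-schedule patients. The restriction comes from naming PAS-full for the summary, not from the citation.

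Fourth, PAS-full might admit a sparse patient if Cmax were derived from the day-8 pre-dose and 3-hour samples. The wording of 3.8.3 allows this. Two-sample maxima would then be pooled with five-sample profiles, so that reading needs clarification too.

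Fifth, the restriction might be a deliberate cut after the futility stop. SAP section 1 says the efficacy and safety analyses were reduced, but it names PK among the analyses performed only now. Section 11 reports no change from the protocol; further text there is redacted.

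**Conclusion.** The inconsistency is real and should be corrected. SAP 9.6.2 contradicts SAP 3.8.3 on Cmin and departs from Protocol 10.5.4 on Cmin and C3h. Followed as written, the Cmin/C3h parameter summary would leave out about 79% to 88% of midostaurin patients, plus full-schedule patients excluded only for vomiting after the first dose. The range assumes that PAS-full equals the full-sampling subset and that between 283 and 502 patients were randomised. There is no consequence for efficacy or for the decision to stop.

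A reader might infer more than the documents support:

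- **That the data are discarded.** They are not: concentrations are summarised and parameters listed.
- **That 88% is the figure for this analysis.** It rests on planned enrolment, whereas this SAP was written after the stop.
- **That confidence intervals would widen.** SAP 9.6.2 plans no PK confidence intervals.
- **That post-consolidation numbers can be projected from the earlier phase III trial (205 of 717 entering that phase).** That rate pools two arms with unequal entry (120 and 85) in FLT3-mutated patients under 60. It also ignores the early stop, and that the full-sampling patients were randomised first and so had longest to reach later phases.

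**What to change.** In SAP 9.6.2, replace the single-population sentence as follows:

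- Summarise AUC0-t (AUC0-12h), AUClast, Cmax and Tmax on PAS-full.
- Summarise Cmin, C3h (where sampled) and by-visit concentrations on PAS-all, applying the same rule to the sum of active moieties.
- Cite Protocol Tables 7-8 and 7-9 together for samples after day 8.

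It would help to state in SAP 3.8.3 whether PAS-full requires the full day-8 schedule. If the PAS-full restriction on Cmin and C3h was intended, SAP section 11 should record it as a change from the protocol, and 3.8.3 should be amended to agree.

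The cost is a sentence or two in the SAP and a change of population flag in the affected tables. No new data are needed.
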